4.5.3 Sample Size and Power Estimate

Since this protocol is for clinical access only, there is no need for sample size and power estimation calculations. It is anticipated that 100 patients will be imaged with primary diagnosis of prostate cancer or biochemically recurrent prostate cancer. There will likely be a ramp up period in the number of patients who will be scanned.

4.5.4 Accrual estimates

Clinically eligible patients with prostate cancer.

5. INVESTIGATIONAL DRUG

5.1 **GA68 PSMA-11**

5.1.1 The PSMA-11 Sterile Cold Kit

The final drug product is the ⁶⁸Ga-PSMA-11 Prostate-Specific Membrane Antigen (PSMA)- prepared using the Telix cold sterile kit labeled with the Gallium-68. The full description of the investigational drug is described in the CMC section of the initial submission packet.

5.1.2 Formulation and preparation

The final dosage form of Ga68-PSMA-11 is an intravenous solution. Ga68-PSMA-11 will be aseptically prepared in the PharmaLogic radiopharmacy as described in the CMC section of the IND. Subject specific doses will be aseptically withdrawn from the vial of the sterile cold kit into a sterile syringe. The radioactive dose will be calibrated for the appropriate scan time with the use of a dose calibrator. The syringe containing the study drug will be placed in a syringe shield with the approved IND prescription label as in the initial IND submission and then delivered to the University of Colorado Anschutz Outpatient Center for PET/CT imaging or the University of Colorado Research Imaging Center (CURIC) for PET / MRI imaging.

5.1.3 Administration

Ga68-PSMA-11 will be administered intravenously with a dose of 2.5 MBq of ⁶⁸Ga per kg body weight with a minimum of 100 MBq (3mCi) and maximum of 300 MBq (7mCi) ⁶⁸Ga per patient.

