To provide clinical access to ⁶⁸Ga-PSMA-11 PET at the University of Colorado. Patients will be monitored for safety.

Secondary Objective(s):

To compare the diagnostic impact of ⁶⁸Ga-PSMA-11 PET/CT imaging over current standard of care imaging modalities.

To compare the impact of ⁶⁸Ga-PSMA-11 PET/CT imaging over standard of care imaging on the therapeutic decision or change in management with regards to the number and/or lesion location and PSA levels.

Exploratory Objective(s):

Obtain preliminary data on accuracy of 68Ga-PSMA-11 PET/CT imaging PET / MRI in patients with intermediate and high-risk prostate cancer patients prior to prostatectomy.

METHODOLOGY	
Study Design	This is a prospective, Phase III, single-center, open-label to provide extended access in patients with biochemically recurrent prostate cancer. Eligible patients will undergo baseline assessments as per the Schedule of Study Activities in Appendix A. Approximately 100 patients are planned for enrollment in this study. Patients will receive a single dose of ⁶⁸ Ga-PSMA-11 and undergo a PET/CT or PET/MRI imaging study.
Intervention	The intervention is a PET scan with the radiolabelled PSMA ligand, ⁶⁸ Ga-PSMA-11. The PET may be combined with a CT scan as a PET/CT or an MRI scan as PET/MRI. ⁶⁸ Ga-PSMA-11 PET/CT will be acquired using a modern digital GE PET/CT scanner or a modern digital PET / MRI scanner.
Intervention Duration	AEs will be collected during injection and uptake phase (45-120 min posts infusion) of Ga-68 PSMA-11 PET/CT scan. All safety events will be recorded up to 120 min post injection.
Population	Men with pathologically proven prostate adenocarcinoma, high risk cancer at diagnosis, evidence of biochemical recurrence, or known metastatic disease planned to start and change systemic therapy regimen
Investigational Agent and Formulation	A description of the components of the PSMA-11 Sterile Cold Kit can be found in Section 5.1 of the protocol and in the initial IND submission.
Dose and Route of Administration	One intravenous catheter will be placed for radiopharmaceutical administration. Patients will be injected with 100 MBq (3mCi)-300 MBq(7mCi) of ⁶⁸ Ga-PSMA-11 via this catheter.

SUBJECT POPULATION	
Number of Patients Planned for Enrollment	Approximately 100 patients are planned for enrollment in this study.

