4.2.3 Selection and Timing of Dose for Each Subject

No specific patient preparation is required before ⁶⁸Ga-PSMA-11 injection. The imaging agent (Ga-68 PSMA-11) will be administered on an outpatient basis. It will be administered a single time intravenously prior to the PET imaging. The injected dose will be 100 to 300 MBq (~3-7 mCi) of ⁶⁸Ga-PSMA-11.

Following a waiting period of 60 minutes post 68Ga-PSMA-11 administration, patients will be scanned from mid thighs to base of the skull. Images will be acquired with patients in a supine position with their arms raised above their head. If patients cannot raise their arms above the head, the arms will be comfortably positioned and secured by the side of the patient. The goal is to administer this amount of the imaging probe labeled with 2.5 MBq of ⁶⁸Ga per kg body weight with a minimum of 100 MBq (3mCi) and maximum of 300 MBq (7mCi) 68Ga per patient. The typical acquisition time per bed position will be 3 min and the typical number of bed positions is 4.

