4.3 PET IMAGING

- a) ⁶⁸Ga-PSMA-11 PET preparation: Oral hydration is recommended on the day of the scan. No fasting is required.
- b) Contrast administration: Imaging contrast will not be ordered as part of this study. However, if a clinically indicated diagnostic CT scan is ordered with intravenous iodinated contrast, it can be added at the end of the ⁶⁸Ga PSMA-11 PET imaging.
- c) Voiding: Voiding is recommended immediately before start of the scan.

- d) ⁶⁸Ga-PSMA-11 injection: The intravenously injected dose will be 100-300 MBq (~3-7 mCi) of ⁶⁸Ga-PSMA-11 PET.
- e) PET imaging protocol: Scan coverage will extend from mid-thigh to the base of the skull, starting from the mid-thighs to minimize urinary bladder radiotracer accumulation at the start of PET imaging. At a minimum, 3 minutes per bed position will be used. In certain circumstances, coverage may be extended to the toes.
- f) Patient monitoring: Patients will be monitored for adverse events during injection and uptake phase of the radiotracer.

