4.4 IMAGE ANALYSIS AND INTERPRETATION

A board-certified nuclear medicine physician or nuclear radiologist on-site will interpret the images of the ⁶⁸Ga-PSMA-11 PET/CT scan. Images will be corrected for attenuation and scatter and adjusted for system sensitivity and will provide parametric images in terms of standardized uptake values (SUV) (= MBq found/gm tissue / MBq injected/gm body mass).

PET imaging can be combined with a low-dose CT for attenuation correction, a diagnostic CT (PET/CT), or MRI (PET/MR). Patients may undergo a diagnostic MRI of the prostate, other body parts or a whole-body MRI at the same imaging session as clinically indicated. Contrast material may be administered for the CT or MRI as clinically indicated.

Imaging will be initiated at approximately 60 minutes (45-120 minutes) following administration of the PSMA radiopharmaceutical. At the discretion of the investigator, an additional image of the pelvis may be obtained.

Patients will receive a single dose of ⁶⁸Ga-PSMA-11 and undergo a PET/CT or PET/MRI imaging study. At the time of interpretation of the ⁶⁸Ga-PSMA-11 PET study, the reviewing nuclear medicine physician and/or radiologist will compare the ⁶⁸Ga-PSMA-11 PET findings with the results from previously performed standard-of-care imaging for prostate cancer staging. The presence or absence of sites suspicious for recurrent prostate cancer will be documented. (e.g., prostate bed, lymph nodes, metastases to bone or other organs).

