6.2.11 EXTENT OF EXPOSURE

A total of 100 patients are planned for exposure to a single dose of ⁶⁸Ga-PSMA-11 at 100MBq (3mCi)-300 MBq (7mCi).

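### The maximum injected activity is given six times as 300 MBq (7 mCi), but 300 MBq is 8.1 mCi and 7 mCi is 259 MBq

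*Combined protocol and SAP*

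**What the plan says.** The limit on injected activity appears six times, each time in both units:

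- Synopsis, Dose and Route of Administration: "Patients will be injected with 100 MBq (3mCi)-300 MBq(7mCi) of"
- Section 4.2.3, first range sentence: "The injected dose will be 100 to 300 MBq (~3-7 mCi) of"
- Section 4.2.3, weight-based rule: "minimum of 100 MBq (3mCi) and maximum of 300 MBq (7mCi) 68Ga per patient"
- Section 4.3, item d: "The intravenously injected dose will be 100-300 MBq (~3-7 mCi) of"
- Section 5.1.3: "minimum of 100 MBq (3mCi) and maximum of 300 MBq (7mCi")
- Section 6.2.11: "at 100MBq (3mCi)-300 MBq (7mCi")

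Sections 4.2.3 and 5.1.3 set the activity within these limits at 2.5 MBq per kg. Table 1 in Section 6.1 gives absorbed and effective dose per MBq. Section 5.1.2 has the radiopharmacy draw up subject-specific doses, measure them in a dose calibrator, and deliver each syringe "placed in a syringe shield with the approved IND prescription label". The protocol reproduces neither that label nor the radiopharmacy order.

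**The concern.** The two figures for the maximum are presented as the same activity, and they are not. This matters more than a slip in background text would, because Section 5.1.3 is the administration instruction and the figure is a per-patient maximum.

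Two things could follow. Staff who work in mCi and stop at 7 would give heavier men less than the weight rule prescribes. And an injected activity between 259 and 300 MBq is within the limit in one unit and above it in the other. Section 6.1 provides for internal audits by the Data and Safety Monitoring Committee and for progress reports that list protocol deviations, so someone may have to classify such a dose. The protocol gives no rule for doing so.

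**Working it through.** **Inputs.** Minimum 100 MBq (3 mCi), maximum 300 MBq (7 mCi) and 2.5 MBq/kg, all from Section 5.1.3. Effective dose 19 μSv/MBq and kidney dose 456 μGy/MBq, from Table 1. The only input from outside the protocol is the definition 1 mCi = 37 MBq.

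**1. Do the stated pairs reproduce?**

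- Minimum: 100 / 37 = 2.70 mCi, which rounds to the stated 3.
- Maximum: 300 / 37 = 8.11 mCi, which rounds to 8, not 7.
- In reverse: 7 × 37 = 259 MBq.
- Gap at the maximum: 300 − 259 = 41 MBq. This is 41 / 300 = 13.7%, or 8.11 − 7 = 1.11 mCi.

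The minimum reproduces after rounding and the maximum does not. Two of the six occurrences (the first range sentence of 4.2.3, and 4.3 item d) put a tilde before the mCi range. A tilde covers rounding; it does not cover 1.1 mCi. The other four have no tilde.

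**2. Who would be dosed differently?** The cap starts to bind at cap / 2.5:

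- 300 / 2.5 = 120 kg
- 259 / 2.5 = 103.6 kg

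Up to 103.6 kg both readings give the same activity.

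**3. By how much?** The shortfall at weight w, if 7 mCi is applied, is min(2.5w, 300) − min(2.5w, 259):

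| Weight (kg) | Cap 300 MBq | Cap 259 MBq | Shortfall (MBq) |
|---|---|---|---|
| 103.6 | 259 | 259 | 0 |
| 110 | 275 | 259 | 16 |
| 120 and above | 300 | 259 | 41 |

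**4. What is that in radiation dose?** At the largest difference:

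- Effective dose: 19 × 300 = 5,700 μSv (5.70 mSv) against 19 × 259 = 4,921 μSv (4.92 mSv), a difference of 0.78 mSv.
- Kidneys: 456 × 41 = 18,696 μGy, or 18.7 mGy.

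**5. Which figure was meant?** The dosing rule is in MBq per kg, MBq comes first at all six places, Table 1 is per MBq, and where a tilde appears it is attached to mCi only. All of this points to 300 MBq. The SUV definition in Section 4.4 ("MBq found/gm tissue / MBq injected/gm body mass") is also written in MBq, but the unit cancels there, so it adds little.

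**The case against.** The strongest reply is that the ceiling is not really open. The operative rule is in MBq, mCi appears only in brackets, and the tilde at two places marks mCi as the approximate unit. On that reading this is a wrong secondary conversion and nobody would be dosed differently. That is the likelier reading, and it keeps the point minor. It does not remove the point: four of the six statements give 7 mCi without qualification, and no sentence gives MBq precedence.

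The consequences are also conditional. They need staff to apply the bracketed figure, in men above 103.6 kg, and the protocol gives no weight distribution from which to say how many men that is. The protocol does not define a dosing deviation in mCi. The worst case is a lower activity that still lies within 100 to 300 MBq, and nothing in the protocol suggests that 259 MBq would be inadequate for imaging. These limits stand.

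Finally, changing the minimum from 3 to 2.7 mCi is a matter of style, since 3 is a fair rounding. That is accepted; it is worth doing only because the same lines are being edited.

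**Conclusion.** The conversion is wrong as written: 300 MBq is 8.1 mCi, and 7 mCi is 259 MBq. The error is repeated six times in five sections, with no correct version anywhere in the protocol.

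The practical effect is zero if MBq is followed. If mCi is followed, it is at most 41 MBq, 0.78 mSv effective dose and 18.7 mGy to the kidneys, and only above 103.6 kg. These figures assume that 2.5 MBq/kg is applied as stated and that the Table 1 coefficients hold. That 300 MBq is the intended ceiling is an inference from the protocol's consistent use of MBq; the IND label or the radiopharmacy order would have to confirm it.

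The safety, detection and change-in-management analyses are untouched, and the protocol states no total radiation dose that becomes wrong. Minor.

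**What to change.** 1. Check the ceiling against the IND prescription label and the radiopharmacy order.
2. If it is 300 MBq, write 300 MBq (8.1 mCi) in the synopsis, both sentences of 4.2.3, 4.3 item d, 5.1.3 and 6.2.11. If 7 mCi was intended, write 259 MBq (7 mCi) at the same places. That second option changes the MBq ceiling itself, so it would be more than a clerical edit.
3. Give the minimum as 100 MBq (2.7 mCi) in the same edit.
4. Add one sentence to 5.1.3 saying that the MBq value governs and that mCi is given for information.

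The cost is one number pair at six places, one sentence, and a check of the dispensing documents. Section 7.3 requires changes after approval by the IRB and the Radiation Safety Committee to be documented as an amendment, so the correction can go into the next one. Enrolment, sample size and analysis do not change.

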6. ADVERSE EVENTS AND REPORTING REQUIREMENTS

6.1 ASSESSMENT OF SAFETY

Pharmacologic effects of ⁶⁸Ga-PSMA-11

⁶⁸Ga-PSMA-11 has been injected for PET imaging in more than 2,616 published patients [11] and the safety profile has been well established. Currently, no serious adverse events related to drug have been reported. This is expected because the mass of compound is minimal, less than 25 micrograms. There is a potential small risk of infection at the site of injection.

Safety evaluation

AEs will be collected during injection and uptake phase (50-100 min) of Ga-68 PSMA-11 PET/CT scan. All safety events will be recorded up to 120 min post injection.

Analyses will be performed for all patients receiving Ga-68 PSMA-11. The study will use the [CTCAE v5.0](#) for reporting of adverse events.

Radiation exposure from PSMA PET/CT imaging

As part of this scan there is radiation delivered from the ⁶⁸Ga and from the low dose CT scan that are performed as part of the PET/CT for attenuation correction and co-registration. Although any exposure to ionizing radiation has the potential to cause some harm to tissue, the radiation exposures in this study are comparable to the low-level exposures associated with common diagnostic procedures such as CT scanning. There remains a low theoretical risk of developing a cancer at some point later in life as a result of the radiation exposure received in this study. This risk is much smaller than the clinical risks posed by the patient's current cancer or the salvage radiation therapy the patient would be receiving. Participants should not father a baby while on this study. Acceptable birth control methods include abstinence, double barrier method, surgically sterilized patient or partner.

In a phase 1 clinical trial (EudraCT: 2016-004971-32) conducted with the PSMA-11 sterile cold kit as Investigational Medicinal Product (IMP), physiological uptake of [68Ga] PSMA-11 was observed in kidneys, urinary bladder, salivary glands and small intestines. The kidneys were the organs receiving the highest absorbed dose. Additional organs with higher dose were the bladder, small intestines, and salivary glands. Estimated radiation absorbed doses in selected organs and tissues are presented in the Table 1 below.

Table 1 summarizes the expected radiation exposure for the planned study and is consistent with biodistribution data published by Afshar-Oromieh et al. [12] and assuming a voiding interval of 2 h, i.e., the patient is asked to void the bladder after completion of the PSMA PET/CT study. ⁶⁸Ga has a short half-life of 68 minutes.

Table 1. Estimated Radiation Absorbed Dose per Injection Activity in Selected Organs and Tissues of Adults after a Gallium (68Ga) PSMA-11 Injection Dose

Absorbed Doses

Organ/Tissue	Estimated Radiation Absorbed Dose per Injection Activity (μGy/MBq)
Adrenals	12
Brain	1
Breasts	6
Gallbladder	12
Lower colon	12
Small intestine	58
Stomach	9
Upper Colon	13
Heart	13
Kidneys	456
Liver	22
Lungs	8
Muscle	8
Pancreas	11
Red marrow	12
Osteogenic cells	13
Skin	6
Spleen	37
Testes	8
Thymus	7
Thyroid	7
Bladder	241
Salivary glands	96
Total body	11
Effective dose	19 (μSv/MBq)

Monitoring and Oversight

The sponsor investigator will be responsible for monitoring the trial per the trial monitoring plan, in addition to overseeing the safety and efficacy of the trial including any specimens collected, executing the data and safety monitoring (DSM) plan, and complying with all reporting requirements to local and federal authorities. This oversight will be accomplished through additional oversight from the Data and Safety Monitoring Committee (DSMC) at the University of Colorado Cancer Center (CU Cancer Center). The DSMC is responsible for ensuring data quality and study participant safety for all clinical studies at the CU Cancer Center, which is the coordinating institution of this trial. A summary of the DSMC's activities is as follows:

- Conduct of internal audits
- Ongoing review of all serious adverse events (SAEs) and unanticipated problems (UAPs)
- May submit recommendations for corrective actions to the CU Cancer Center's Executive Committee

Per the CU Cancer Center Institutional DSM Plan, SAEs and UAPs are reported to the DSMC, IRB and the sponsor investigator per protocol. All SAEs and UAPs are to be reported to the DSMC within 7 (for fatal or life-threatening events) or 15 (non-life-threatening events) calendar days of the sponsor investigator receiving notification of the occurrence.

Each subject's treatment outcomes will be discussed by the site PI and appropriate staff at regularly scheduled meetings. Data regarding number of subjects, significant toxicities, dose modifications, and treatment responses will be discussed and documented in the meeting's minutes.

The sponsor investigator will provide a DSM progress report to the CU Cancer Center DSMC on a recurring basis (either every six or twelve months based on DSMC vote). The DSM report will include a protocol summary, current enrollment numbers, summary of toxicity data to include specific SAEs, UAPs and AEs, any dose modifications, all protocol deviations, and protocol amendments. The DSM progress report submitted to the DSMC will also include, if applicable, the results of any efficacy data analysis conducted. Results and recommendations from the review of this progress report by the DSMC will then be provided to the sponsor investigator in a DSMC review letter. The sponsor investigator is then responsible for ensuring this letter is submitted to the site's IRB of record at the time of IRB continuing review.

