Major Inclusion Criteria	
Patients must meet all inclusion criteria to be considered eligible for participation in the study.
 
• Histopathologically proven prostate adenocarcinoma.• Age \geq 18 years• 1) Patients with newly diagnosed with prostate cancer: Primary Staging: high / intermediate risk per NCCN guidelines or 2) Biochemical Recurrence: Rising PSA after definitive therapy with prostatectomy or radiation therapy (external beam or brachytherapy) or other local therapies:
• Post radical prostatectomy (RP) – AUA recommendation PSA greater than or equal to 0.2 ng/mL measured more than 6-13 weeks after RP and confirmed by a second determination of a PSA level of >0.2 ng/mL• Post-radiation therapy – ASTRO-Phoenix consensus definition Nadir + greater than or equal to 2 ng/mL rise in PSA• After Local Therapies Nadir + greater than or equal to 2 ng/mL rise in PSA or3) Metastatic prostate cancer, castrate naïve or castrate resistant:
• To confirm suspected metastatic disease in patients with recurrent prostate cancer• To assess treatment response of metastatic disease• Ability to understand a written informed consent document, and the willingness to sign it.

Name of Sponsor		[name]
Investigational Product		68 Ga-PSMA-11 prepared using a PSMA-11 Sterile Cold Kit
Major Exclusion Criteria	
• Unable to lie flat, still or tolerate a PET/CT scan, or any other condition that would preclude PET/CT imaging.• Patients with any medical condition or circumstance that the investigator believes may compromise the data collection or lead to a failure to fulfil the study requirements.• Patients with known hypersensitivity to the active substance or to any of the excipients of the investigational product.	
ASSESSMENTS		
Efficacy	Standard of care imaging, clinical assessment, PSA.	
Safety	Safety of the drug has been established (11). AEs will be collected during injection and uptake phase (45-120 min post infusion) of Ga-68 PSMA-11 PET/CT scan. All safety events will be recorded up to 120 min post injection.	

TABLE OF CONTENTS

SYNOPSIS.....	4
ABBREVIATIONS AND DEFINITIONS	10
1. BACKGROUND AND RATIONALE	11
1.1 Name and Description of Investigational Product.....	13
1.2 Results of Nonclinical Studies	13
1.3 Results of Clinical Studies	13
2. STUDY OBJECTIVES.....	13
2.1 Primary Objective	13
2.2 Secondary Objectives.....	13

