3. ENDPOINTS

3.1.1 Primary Objective

Evaluate the safety and tolerability of ⁶⁸Ga-PSMA-11 using the following primary safety outcome measures: Incidence and nature of AEs and change in clinical laboratory results. Incidence and severity of AEs and adverse events will be estimated with 95% confidence intervals summarized with descriptive statistics.

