4.2 PATIENT ASSESSMENTS

4.2.1 Symptom assessment pre- and post-imaging

A directed review of symptoms (nausea, fatigue, pain) will be graded against CTCAE to provide baseline evaluation prior to injection and assess for adverse events post-injection.

4.2.2 Change in management surveys.

Referring clinicians will be queried in providing information on how PSMA PET/CT results impacted the clinical management of patients.

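### Minor: the adverse-event recording window for the primary safety outcome is internally inconsistent. Recording stops at 120 minutes, while imaging may start as late as 120 minutes and post-scan monitoring has no stated time.

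*Combined protocol and SAP*

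**What the plan says.** Sections 3.1.1 and 4.5.1 set the "primary safety outcome measures: Incidence and nature of AEs and change in clinical laboratory results". They ask for 95% confidence intervals but give no time window for the events.

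The window is given elsewhere, and not always in the same way:

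- **Stop.** Section 6.1 says "All safety events will be recorded up to 120 min post injection". The synopsis says the same under Intervention Duration and under Safety.
- **Collection phase.** The synopsis Safety row says "AEs will be collected during injection and uptake phase (45-120 min post infusion) of Ga-68 PSMA-11 PET/CT scan". Section 6.1 gives the same phase as 50-100 minutes. Section 4.3(f) gives no times: "Patients will be monitored for adverse events during injection and uptake phase of the radiotracer". It does not name the scan.
- **Start of collection.** Section 6.2.1 starts AE collection when consent is signed. It calls an event treatment emergent if it follows administration, with no end point.
- **After imaging.** Section 4.2.1 plans a symptom review "to provide baseline evaluation prior to injection and assess for adverse events post-injection". Appendix A marks safety monitoring on the day of the scan and again in a Post Scan column that has no time.

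On imaging, section 4.4 says "Imaging will be initiated at approximately 60 minutes (45-120 minutes) following administration". Section 4.2.3 says "The typical acquisition time per bed position will be 3 min and the typical number of bed positions is 4", and section 4.3(e) adds "At a minimum, 3 minutes per bed position will be used".

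**The concern.** A scan that follows the protocol can run past the point at which the protocol stops recording safety events. If it starts at 120 minutes, the whole scan falls after the stop. Section 6.2.6 expects discomfort from lying in the camera, such as back pain, and that arises during the scan.

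The second difficulty does not depend on start time. The Post Scan monitoring in Appendix A may be the symptom review of section 4.2.1, done before the patient leaves, or it may be a later contact. If it falls after 120 minutes, the plan schedules an assessment whose findings its own recording rule excludes.

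What is at stake is the all-cause AE incidence and its confidence interval, which are primary results. The analysis is descriptive, so no hypothesis test is affected.

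**Working it through.** The plan has no figure of its own to reproduce, since section 4.5.3 says no sample-size calculation is needed. The check is timing arithmetic on the plan's inputs.

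**Inputs**

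- Recording stop: 120 min post injection (synopsis, 6.1).
- Permitted imaging start: 45 to 120 min, target about 60 min (4.4; 60-minute wait in 4.2.3).
- Scan: typically 4 beds at 3 min (4.2.3), where 3 min is a minimum (4.3(e)).
- Planned patients: 100 (4.5.3, 6.2.11).

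**Timing**

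- Shortest 4-bed scan: 4 × 3 = 12 min.
- Latest start that ends by the stop: 120 − 12 = 108 min.

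| Scan start (min) | Scan end (min) | Past the stop (min) |
|---|---|---|
| 45 | 57 | 0 |
| 60 | 72 | 0 |
| 108 | 120 | 0 |
| 109 | 121 | 1 |
| 120 | 132 | 12 |

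- Margin at the target start: 120 − 72 = 48 min.
- Imaging needed to pass the stop from a 60-min start: more than 120 − 60 = 60 min, that is, more than 60/3 = 20 beds.
- Share of the permitted start range that overruns: (120 − 108)/(120 − 45) = 12/75 = 16%. This is a share of the range, not of patients.

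The 12 minutes counts bed time only. The plan also allows coverage to the toes and a contrast CT after the PET (4.3), and an extra pelvic image or an MRI in the same session (4.4). It gives no durations for these. If extended coverage took 5 to 8 beds (an assumption), the scan would last 15 to 24 min and the latest covered start would be 105 to 96 min.

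**Post-scan monitoring**

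After a scan at the target time, a review within 48 minutes of the scan's end falls inside the stop, and a later one falls outside it. Because Appendix A gives no time, the documents do not say which applies.

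**Scale of one omitted patient**

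With 100 patients, leaving out one patient's only AE lowers incidence by 1/100 = 1 percentage point. The plan names no interval method; exact Clopper-Pearson limits are assumed here.

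- 1/100: 95% CI 0.03% to 5.4%.
- 0/100: 95% CI 0% to 3.6%, where the upper limit is 1 − 0.025^(1/100) = 0.036.

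This illustrates scale only. No figure in the documents predicts such an event.

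**The case against.** The strongest reply is that the plan does have a rule. The 120-minute stop appears three times in the same terms, and in section 6.1 it stands directly before the statement of who is analysed. Sections 3.1.1 and 4.5.1 need not repeat it. This stands: the stop is the natural window for the primary count. A reader might infer that the primary outcome has no window at all, and the documents do not support that.

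It can also be said that a window tied to injection suits an outcome about the tracer, and that nothing requires it to contain the scan. That is a fair design position. It does not explain why the same plan schedules post-imaging assessment, lists camera discomfort as an expected event, and leaves the treatment-emergent definition open-ended.

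The consequence is also limited. The target start leaves 48 minutes to spare, and no section suggests that starts after 108 minutes are expected. Section 6.2.5 asks for a separate causality judgement for study conduct, so camera discomfort can be told apart from a reaction to the tracer. That separates events once they are recorded; it does not recover events that were never recorded.

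The other differences weigh less. Both uptake ranges, 45-120 and 50-100 minutes, lie inside the shared stop. The treatment-emergent definition and the baseline symptom review largely settle how pre-injection events are handled, although sections 3.1.1 and 4.5.1 do not refer to that definition.

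**Conclusion.** The inconsistency is real and minor. It has two parts: a 4-bed scan started after 108 minutes outlasts the recording stop, and the untimed Post Scan monitoring conflicts with the stop whenever it falls after 120 minutes, whatever the start time. Under the natural reading, events found in either situation are left out of the primary count, and these would mainly be non-serious and related to study conduct.

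Two stronger inferences should be resisted. One is that 16% of patients are affected: the documents give no distribution of start times and no time for Post Scan monitoring, so the number cannot be calculated. The other is that serious harm would go unreported: section 6.2.2 requires SAE reporting from consent with no stated end, and section 6.2.3 covers related deaths within 30 days of administration. The effect on conclusions about tracer safety is likely small.

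The 108-minute figure rests on the typical 4 beds at the minimum 3 minutes each. Any longer session makes the cut-off earlier.

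**What to change.** Reconcile the synopsis (Intervention Duration and Safety), sections 4.2.1, 4.3, 4.4, 6.1 and 6.2.1, and Appendix A to one AE recording window, worded the same throughout:

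- Run the window to the later of 120 minutes post injection and the end of the imaging session, including the section 4.2.1 post-imaging symptom review on the day of the scan.
- State whether Post Scan safety monitoring in Appendix A is that review or a later contact.
- State in sections 3.1.1 and 4.5.1 that the primary outcome counts treatment-emergent AEs, as defined in 6.2.1, in that window. List pre-injection and later-reported events separately.
- Give one uptake range in the AE-collection wording of the synopsis and section 6.1.
- Leave SAE and death reporting (6.2.2, 6.2.3) unchanged.

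The cost is mainly redrafting. The post-imaging review is already planned, so no visit or procedure is added, though recording continues past 120 minutes when a session runs late. Reported AE incidence may be slightly higher.
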